Discontinuation criteria:	
Trial discontinuation means the clinical trial is not completed according to protocol and is prematurely discontinued. The main purpose of trial discontinuation is to protect the rights and interests of the subjects, ensure the quality of the trial, and avoid unnecessary economic losses.
 
(1) If serious safety issues occur during the trial, the trial should be discontinued in time;
 
(2) During the trial, major errors are found in the clinical trial protocol that make evaluation of drug efficacy difficult; or major deviations from the well-designed protocol are found in the implementation that make evaluation of drug efficacy difficult if the trial is to be continued;
 
(3) The sponsor requests to discontinue the trial (because of economic or management factors or others);
 
(4) The administrative department in charge rescinds the trial.

Dose design and treatment regimen:	
Patients will receive local rectal short-course radiotherapy. Radiotherapy will employ conformal or intensity-modulated radiation therapy, with a pelvic irradiation dose of 25 Gy/5 Fractions/1 week. Then rest for 1 week after radiotherapy and begin to receive neoadjuvant chemotherapy CAPOX and PD1 inhibitor for immunotherapy, for 2 cycles. One week after the completion of neoadjuvant therapy, a second evaluation on the primary lesions will be performed, and the surgical method is total mesorectal excision. Postoperative adjuvant therapy will be started 3-4 weeks after surgery, and the treatment regimen will be determined by the investigator. The efficacy of neoadjuvant therapy on postoperative specimens will be evaluated in accordance with Rectal Cancer Regression Grade. Treatment-related toxic and side effects will be evaluated as per CTCAE 5.0 toxic and side effects evaluation criteria.

Statistical method:	
This study will employ SPSS 16.0 statistical software package for analysis. EFS and OS will be analyzed using the Kaplan-Meier method and log-rank test.

Trial schedule:	
Estimated start time of the trial: Oct. 2019
 
Estimated time of enrollment completion: Oct. 2021
 
Estimated end time of the trial: Dec. 2025

Version No.:	V2.0

Clinical Study Protocol

Version No.: V2.0

List of Abbreviations

Abbreviations and statistics descriptions (English)

dMMR	Deficient mismatch repair protein
MSI	Microsatellite instability
mCRC	Metastatic Colorectal Cancer
PD-1	Programmed cell death protein 1

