4.3 Removal criteria

Subjects who do not meet the inclusion criteria but are enrolled should be rejected, including: (1) misdiagnosis; (2) mistaken enrollment; (3) having not taken the medication; (4) having no evaluation records.

The reason of rejection should be explained for all rejected subjects, and their medical history in the study should be reserved for future reference. However, subjects who have received at least one treatment and have at least one safety record can be included in the safety analysis.

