According to the previous studies, the pCR rate after preoperative CRT in patients with LARC is approximately 15%. We expected that the regimen of SCRT combined with subsequent chemotherapy and camrelizumab could increase the pCR rate from 15% to 40%. A sample size of 24 patients was required to provide at least 80% power to detect this estimated improvement, in one-sided χ^2 -test with a significance level of 2.5%, and a 20% dropout was considered, resulting in that a total sample size of 30 patients was planned for this study.

Statistical analyses were conducted using SAS® software (version 9.2, SAS Institute Inc, Cary, USA). Continuous variables were summarized using medians and ranges, and categorical variables were described using the frequency and percentage. Baseline and safety analyses were performed for all enrolled patients (intention-to-treat [ITT] population), and efficacy analyses were conducted for those who administrated at least 1 dose of camrelizumab (full analysis set [FAS] population). P value of less than 0.05 was considered statistically significant.

The exploratory objective is: to evaluate the relation of biomarkers (e.g. PD-L1 and MSI) in tumor tissues and/or blood to PD1 efficacy and pCR. Biomarker detection will be carried out with the treated tissue and/or blood obtained prior to treatment.

Continuous variables that conform to normal distribution will be expressed as mean +/- standard deviation, minimum value and maximum value, and those do not conform to normal distribution will be expressed as median; categorical variables will be described in frequency and percentage, and 95% confidence interval will be calculated if necessary. Mean values between the two groups will be compared by t test, and the rates between the two groups will be compared by chi-square test. Survival analysis will be performed by the Kaplan-Meier method. Comparison between groups will be performed by bilateral log-rank test. All tests are two-sided, and 0.05 is taken as the level of the tests.

9. Adverse Event Monitoring

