11.1 Data analysis set

Full analysis set (FAS): includes those who were administrated at least one dose of camrelizumab. When a primary efficacy indicator is missing, the previous result should be carried forward according to the principle of an intention to treat analysis. The missing values of comparability analysis and secondary efficacy indicators should not be subjected to data-carry-forward, and should be analyzed based on the actual data.

Per protocol set (PPS): includes subjects who meet the inclusion criteria, do not meet the exclusion criteria and have completed the treatment regimen, that is, those who meet the trial protocol, have good compliance and have filled all required sections of the CRF are included in the PPS analysis. In this trial, subjects who drop out after half of the treatment course due to aggravation should be included as invalid subjects in the PPS analysis.

Safety set (SS): subjects who have received at least one treatment and have actual safety assessment data. The missing safety data should not be subjected to data-carry-forward; some rejected subjects who are evaluable can be included, such as those with ages beyond the inclusion criteria, but excluding those who cannot be evaluated for safety due to the use of prohibited drugs. The number of subjects in the SS will be used as the denominator for the incidence of ARs.

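### Efficacy is analysed only in patients who reach a first camrelizumab dose, about two weeks after trial radiotherapy begins, so patients lost in between leave the pCR, EFS and OS denominators

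*Protocol*

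**What the plan says.** Section 8.2 (Statistical analysis) gives the efficacy population: "efficacy analyses were conducted for those who administrated at least 1 dose of camrelizumab (full analysis set [FAS] population"). Section 11.1 says the same: "Full analysis set (FAS): includes those who were administrated at least one dose of camrelizumab".

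The all-enrolled set has a different use in 8.2: "Baseline and safety analyses were performed for all enrolled patients (intention-to-treat [ITT] population"). The safety set in 11.1 takes in "subjects who have received at least one treatment and have actual safety assessment data".

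The synopsis (Dose design and treatment regimen) prescribes 25 Gy in five fractions over one week, and continues: "Then rest for 1 week after radiotherapy and begin to receive neoadjuvant chemotherapy CAPOX and PD1 inhibitor for immunotherapy". The primary objective in section 2, the regimen listed in section 5.1 and the hypothesis in 8.2 all treat SCRT, chemotherapy and the PD-1 inhibitor as one regimen.

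The other rules in 11.1 do not widen the efficacy set. The carry-forward rule sits inside the FAS definition: "When a primary efficacy indicator is missing, the previous result should be carried forward according to the principle of an intention to treat analysis". The per-protocol set is narrower, since its members must "have completed the treatment regimen, that is, those who meet the trial protocol, have good compliance".

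**The concern.** Leaving out patients who never start study treatment can be defended in a single-arm trial. Here study treatment starts with the first radiotherapy fraction, so entry to the FAS depends on something that happens after treatment has begun and that may be related to outcome. A patient who progresses or dies in that window cannot be a pCR and would be an EFS or OS event, but is counted in none of the three. The same patient does count for safety.

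There is no control arm in which similar losses could offset this. The pCR rate is judged against a fixed 15%, and with 30 patients one or two changes in the denominator can matter. The protocol plans no efficacy analysis of everyone who started treatment, even as a sensitivity analysis, and it applies the language of intention to treat to a set selected after treatment start.

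**Working it through.** **Inputs.** From 8.2: null pCR 15%, target 40%, one-sided 2.5%, 24 evaluable, 20% dropout, 30 enrolled, one-sided chi-square test. From the synopsis: one week of SCRT plus one week of rest, so the first camrelizumab dose falls about two weeks after SCRT starts. The protocol does not give the chance d of starting SCRT but never reaching camrelizumab; it is an assumption throughout.

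**The plan's own figure.** Exact binomial, n=24, success if at least 8 pCR: P(X≥8 | 24, 0.15) = 0.0199 and P(X≥8 | 24, 0.40) = 0.808. Then 24/(1−0.20) = 30. The sample size reproduces; the problem lies in the analysis set.

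**Type I error on the FAS.** Assume a true pCR rate of 15% among all 30 starters and that every excluded patient is non-pCR. Then:

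- FAS size n ~ Bin(30, 1−d)
- responders given n ~ Bin(n, 0.15/(1−d))
- type I error = Σₙ P(n) × P(X ≥ c(n) | n, 0.15/(1−d))

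For the exact test, c(n) is the smallest r with P(X≥r | n, 0.15) ≤ 0.025. For the uncorrected chi-square test it is the smallest r with (r/n − 0.15)/√(0.15×0.85/n) ≥ 1.96. To separate selection from the integer cut-off, the last column repeats the exact calculation with the FAS rate held at 15%, that is, with losses unrelated to outcome.

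| d | exact | chi-square | exact, no selection |
|---|---|---|---|
| 0 | 1.0% | 2.8% | 1.0% |
| 2% | 1.7% | 3.2% | 1.5% |
| 5% | 2.3% | 4.4% | 1.7% |
| 10% | 2.8% | 6.0% | 1.5% |
| 20% | 4.8% | 9.5% | 1.4% |

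The exact-test error passes 2.5% only near d=7%. The 1.0% on all 30 is low partly because the cut-off there is 10 of 30, against 9 of 29.

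**Can a few exclusions change the decision?** One-sided p against 15%:

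- Exact test: 9/30 gives 0.028 and 9/29 gives 0.022, so one exclusion is enough.
- Uncorrected chi-square: 9/30 gives z = 0.15/√(0.1275/30) = 2.30, p = 0.011, already significant. With 8 responders, 8/30 gives z = 1.79, p = 0.037, and 8/28 gives z = 2.01, p = 0.022, so two exclusions are enough.

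**EFS and OS.** If k of 30 are excluded and all of them have an event, the all-starter 3-year rate equals the FAS rate × (30−k)/30: ×0.967 for k=1 and ×0.90 for k=3.

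**The case against.** The strongest reply is that the effect may be small. The window is about two weeks, and the protocol gives no reason to expect many losses in it. At d of 5% or less the exact test stays within 2.5%, and all-enrolled baseline reporting would show how many patients were left out. This stands as a limit on size. It does not put the patients back into the denominator.

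Four stronger readings are tempting and are not supported:

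- **That the excluded patients are all early failures.** Section 4.4 also lists protocol deviation and patient request, and some SCRT-only patients could go on to surgery. Upward bias is probable, not certain; that every excluded patient is non-pCR is an assumption of the illustration.
- **That one exclusion at nine responders reverses the result under the plan.** This holds for the exact test only. Under the chi-square test named in 8.2, 9/30 is already significant (p = 0.011, or 0.020 with continuity correction).
- **That the planned 20% dropout measures the loss.** That figure covers the whole trial, so placing all of it before the first camrelizumab dose is an extreme case.
- **That section 4.3 also removes SCRT-only patients.** Its item "3) having not taken the medication" belongs to a list introduced as enrolled subjects who fail the inclusion criteria, so its reach to an eligible irradiated patient is doubtful. The point does not depend on it.

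**Conclusion.** The point holds. Sections 8.2 and 11.1 fix an efficacy set that omits patients who began the regimen under test but did not reach its third component, and nothing else in the protocol restores them. The direction probably favours the regimen; the size cannot be fixed from the protocol. Under the stated assumptions, a 5% loss moves the exact-test type I error to 2.3% (1.7% without selection) and the uncorrected chi-square error from 2.8% to 4.4%. At 10% loss the figures are 2.8% and 6.0%. A decision near the boundary can turn on one or two exclusions, depending on the test. A reader might infer that the sample size is also wrong, but 24 and 30 reproduce. The 20% inflation protects power when patients are dropped; it does not remove the selection. The change should be made, though the trial's conclusions would not necessarily alter.

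**What to change.** In sections 8.2 and 11.1:

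1. Define the primary efficacy set as all enrolled patients who received at least one fraction of SCRT.
2. Count patients in that set who never reach camrelizumab and have no ypT0N0 specimen as not pCR.
3. Include the same patients in the EFS and OS analyses.
4. Keep the set with at least one camrelizumab dose as a labelled sensitivity analysis.

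How camrelizumab-treated but unresected patients are counted, and the time origin for EFS and OS, are separate questions that this change does not settle.

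The cost is wording only, with no new data. The downside is a less favourable pCR rate and lower power if patients are lost early. With 40% pCR among those dosed and 5% early loss, the all-starter rate is 0.40×0.95 = 38%. Exact-test power is then P(X≥10 | 30, 0.38), about 76%, on all 30, against about 85% on the FAS. Part of that difference is the advantage the FAS gains by leaving early losses out.

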Primary objective: The primary objective is to evaluate the efficacy of preoperative short-course radiotherapy combined with neoadjuvant chemotherapy and PD1 inhibitor in the treatment for locally advanced rectal cancer

Secondary objective: The secondary objective is to evaluate the safety of preoperative short-course radiotherapy combined with neoadjuvant chemotherapy and PD1 inhibitor in the treatment for locally advanced rectal cancer

Exploratory objective: To evaluate the relation of biomarkers (e.g. PD-L1 and MSI) in tumor tissues and/or blood to PD1 efficacy and pCR

3. Study Design

A prospective, single-arm, phase II clinical trial.

4. Selection and Withdrawal of Subjects

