11.2 Statistical analysis plan

Statistical analysis should employ the two-sided test, and $P \leq 0.05$ indicates a statistically significant difference (unless otherwise specified).

The Continuous data should be statistically described by mean, median, standard deviation, maximum value, and minimum value; the categorical data or ranked data should be statistically described by frequency.

The test should be used to compare the Continuous data between the groups, and the χ^2 test or rank sum test should be used to compare the categorical data between the groups.

Efficacy evaluation method: the evaluation of primary efficacy evaluation indicator: the overall response rate between the experimental group and the control group should be compared by the superiority test. Hypothesis test is

$$H_0: \pi_T = \pi_C, H_1: \pi_T > \pi_C$$

The 95% CI of the difference in overall response rate between the experimental group and the control group should be calculated, and the lower limit > 0 can be considered as the establishment of superiority. Meanwhile, CMH- χ^2 with central effect should be used for comparison between groups.

Safety evaluation methods: the χ^2 test/Fisher's precision probability test should be used to compare the incidence rates of all adverse events, severe adverse events and adverse reactions between the two groups, and the normal/abnormal changes in laboratory test results before and after treatment should be described.

SAS 9.2 software should be employed for statistical analysis, and the analysis process should be all programmed.

12. Quality control of the clinical trial

(1) The preparation of test vesicle packaged chemotherapeutic drugs provided by the sponsor should conform to the relevant regulations and conditions and be subject to strict quality control.

(2) In the process of clinical study, the clinical research associate assigned by the sponsor should visit the study hospital regularly and faithfully make the inspection records to ensure that the study protocol is strictly followed and all CRFs can be filled in accurately.

(3) The laboratory tests should be conducted by study sites in accordance with the standard operating procedures (SOP). The testing methods and quality control of different study sites should be unified.

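### The chi-square test is the only test named for comparing pCR between small marker groups in about 30 patients; the exact test named elsewhere should cover these tables too (minor)

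*Protocol*

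**What the plan says.** Section 3 describes the trial as "A prospective, single-arm, phase II clinical trial". Section 2 sets an exploratory objective, which section 8.2 repeats under Statistical analysis: "to evaluate the relation of biomarkers (e.g. PD-L1 and MSI) in tumor tissues and/or blood to PD1 efficacy and pCR". The paragraph after that statement says that "the rates between the two groups will be compared by chi-square test", and closes with "All tests are two-sided, and 0.05 is taken as the level of the tests". It gives no alternative for small expected counts and does not say whether the chi-square statistic is continuity-corrected. Confidence intervals are offered only where they are thought necessary.

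Section 11.2 takes the same line for categorical data in general: the chi-square "test or rank sum test should be used to compare the categorical data between the groups". It names Fisher's exact test once, as an alternative to chi-square for comparing incidences of adverse events and adverse reactions.

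On size, section 8.2 states that "A sample size of 24 patients was required to provide at least 80% power to detect this estimated improvement" and that, after dropout, "a total sample size of 30 patients was planned for this study".

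**The concern.** A single-arm trial has no treatment groups to compare. The two-group sentence follows directly on the biomarker objective, so its evident use is marker-positive against marker-negative patients on pCR. With about 30 patients and a minority marker, the resulting 2×2 tables are sparse. Section 1 calls MSS the majority, so MSI, one of the two markers named in the objective, is such a case.

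The protocol thus names an exact test where it compares adverse events, but only a large-sample test where the tables are likely to be sparsest. At stake is how far a nominally significant marker association can be trusted. One or two patients could produce a result below 0.05 that the exact calculation does not support. No primary or secondary endpoint is affected.

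**Working it through.** **Inputs.** From section 8.2: 30 enrolled, 24 evaluable, expected pCR 40% against 15%, tests two-sided at 0.05. Not in the protocol, so assumed: 1 to 5 carriers of a minority marker among 30.

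**The plan's own figure.** An exact binomial test with n = 24 that rejects at 8 or more pCRs has one-sided error 0.0199 at 15% and power 0.808 at 40%. Allowing for dropout, 24/0.8 = 30. The planned numbers reproduce, so 30 is a sound basis for what follows.

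**Expected counts.** With m carriers and pCR 40%, the smallest expected count is 0.40 × m, which is 0.4, 0.8, 1.2, 1.6 and 2.0 for m = 1 to 5. It stays below 5 until the smaller group has 13 patients (0.40 × 12 = 4.8; 0.40 × 13 = 5.2).

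**One table in full.** Let 2 of 2 carriers and 8 of 28 others reach pCR, so a = 2, b = 0, c = 8, d = 20.
- Uncorrected: N(ad − bc)² / [(a+b)(c+d)(a+c)(b+d)] = 30 × 40² / (2 × 28 × 10 × 20) = 48,000 / 11,200 = 4.286, p = 0.038.
- Continuity-corrected: 30 × (40 − 15)² / 11,200 = 1.674, p = 0.196.
- Fisher: the chance that both carriers fall among the 10 responders is (10 × 9)/(30 × 29) = 90/870 = 0.103. No other table with these margins is as improbable, so the two-sided p is also 0.103.

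**Other tables, uncorrected chi-square against Fisher.**

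| Carriers with pCR | Others with pCR | Chi-square p | Fisher p |
|---|---|---|---|
| 1/1 | 5/29 | 0.042 | 0.200 |
| 3/3 | 9/27 | 0.025 | 0.054 |
| 4/5 | 8/25 | 0.046 | 0.128 |
| 4/4 | 8/26 | 0.0085 | 0.018 |

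The first three change sides of 0.05; the last does not.

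**Error given the realised margins** (hypergeometric, N = 30, uncorrected chi-square at nominal 5%).

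| Carriers | High point | Nearby pCR counts |
|---|---|---|
| 1 | 20% at 6 pCRs | 0% at 7 |
| 2 | 10.3% at 10 pCRs (8.3% at 9) | 0% at 11 and 12 |
| 5 | 12.8% at 12 pCRs | 4.7% at 11, 3.1% at 10 |

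The 20% entry is simply 6/30: whenever the single carrier responds, the statistic is 30 × 24² / (1 × 29 × 6 × 24) = 4.138, above the 3.841 cut-off. With 7 pCRs it is 30 × 23² / (1 × 29 × 7 × 23) = 3.399, and rejection is impossible.

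**Error averaged over the pCR count** (all tables enumerated as two binomials with a common rate, N = 30, pCR 40%).

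| Carriers | 1 | 2 | 3 | 4 | 5 |
|---|---|---|---|---|---|
| Chi-square, uncorrected | 0.3% | 2.4% | 3.4% | 4.3% | 5.5% |
| Fisher | 0.0% | 0.2% | 1.2% | 2.0% | 2.6% |

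For smaller groups of 6 to 15 patients the chi-square size at 40% pCR is 4.8% to 5.6%. Over pCR rates of 25% to 55% it does not exceed about 5.8% for any split. Clear inflation at a rate the protocol mentions appears with one carrier and a true pCR of 15%: 11.1% with 30 patients, 11.2% with 24.

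**The case against.** A reader might infer that the chi-square test will generally produce false positives here, and for MSI in particular. The figures do not support that. At the protocol's expected pCR the averaged error is below 5% for 1 to 4 carriers and 5.5% for 5. The high conditional values are peaks, and neighbouring margins give far less or nothing. At 12 pCRs of 30, which is exactly 40%, a marker with one or two carriers cannot reach significance at all.

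Three further objections carry weight. The 0.038 depends on the uncorrected statistic, and the protocol does not say which form is meant; the corrected form gives 0.196, more conservative than Fisher. Section 8.2 never ties its two-group sentence to biomarkers. Section 11.2 refers to a control group that this trial does not have, so the wording may be left over from a two-arm template. Fisher's test also pays for its guarantee with a size well under 5%, so the choice is partly one of preference. Section 13 assigns a statistical analysis plan to a statistician, who could settle the matter there.

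Two things remain. The protocol does not leave the test open: it names one, and names an exact alternative for another purpose only. And all markers share one realised pCR count. Section 8.2 also describes a 418-gene panel. If those genes are compared with pCR, an inference again, averaging over pCR counts does not describe what happens in this trial. With 10 pCRs every two-carrier gene would carry a 10.3% error, and with 12 pCRs none.

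**Conclusion.** The point holds as a minor correction. The chi-square approximation is unreliable in the tables this trial is likely to yield for a minority marker, and single uncorrected p-values can be less than half the exact ones and cross 0.05. Given the realised pCR count, error ran from 0% to 20% in the cases examined. A general excess of false positives is not shown.

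The conclusion rests on three assumptions: that the two groups are biomarker groups, that a minority marker has 1 to 5 carriers among about 30 patients, and that the chi-square statistic is uncorrected. With the continuity correction the risk of spuriously small p-values goes, but the test becomes more conservative than Fisher's in the worked example. Severity is low because the objective is exploratory and the primary pCR result does not depend on it.

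**What to change.** In section 8.2 (Statistical analysis) and section 11.2, state that biomarker-by-pCR tables are tested with Fisher's exact test, and say outright that these are the two-group comparisons meant. Report the pCR rate in each marker group with an exact 95% confidence interval as a matter of course. The interval shows how little a very small group can say: for 2 of 2, the lower exact limit solves p² = 0.025, so p = 0.158, and the interval runs from 15.8% to 100%.

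The change takes about one line in each section, needs no extra data and uses a test that the protocol already names. Its price is conservatism: at 40% pCR the size of Fisher's test is about 0% to 2.6% for 1 to 5 carriers, so fewer associations will reach nominal significance. For an exploratory aim, estimates with exact intervals should carry most of the message.
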